#### 6. TREATMENT PLAN

#### 6.1. Treatment Administration

For Part 1 of the study, AML patients will be stratified by previously untreated vs. treated for AML. There are no stratification factors for MDS patients. All patients will be randomized 1:1:1 to receive one of the following dosing schedules:

7-day low dose (Arm A): 200 mg b.i.d. x 7 consecutive days (Day 1-7) every 4 weeks

7-day high dose (Arm B): 300 mg b.i.d. x 7 consecutive days (Day 1-7) every 4 weeks

3-day high dose (Arm C): 400 mg b.i.d. x 3 consecutive days per week for 2 weeks (Day 1-3, 8-10) every 4 weeks

For Part 2 of the study: AML patients will receive sapacitabine at 300 mg b.i.d. x 3 consecutive days per week for 2 weeks every 4 weeks

For Part 3 of the study: AML patients will be stratified by prior treatment with decitabine for the preceding MDS (Yes or No) and randomized 1:1:1 to receive one of the following 3 dosing schedules:

Arm D: 200 mg b.i.d. x 7 consecutive days every 4 weeks

Arm E: 300 mg q.d. x 7 consecutive days every 4 weeks

Arm F: 300 mg b.i.d. x 3 consecutive days per week for 2 weeks every 4 weeks

For Part 4 of the study: MDS patients will be stratified by prior treatment with decitabine for MDS (Yes or No) and randomized 1:1:1 to receive one of the following 3 dosing schedules

Arm G: 200 mg b.i.d. x 7 consecutive days every 4 weeks

Arm H:  $300 \text{ mg } q.d. \times 7$  consecutive days every 4 weeks

Arm I: 100 mg q.d. x 5 consecutive days per week for 2 weeks every 4 weeks

Treatment will begin within 7 days of randomization or registration and be administered orally on an outpatient basis unless the patient is hospitalized for reasons other than drug-related toxicities. Patients who are assigned to *b.i.d.* dosing will receive two doses of sapacitabine per day, approximately 12 hours apart. Sapacitabine should be taken within one hour prior to a meal, if possible. Patients who are assigned to *q.d.* dosing will receive one dose of sapacitabine per day which should be taken within one hour prior to breakfast if possible. Patient compliance with study medication will be monitored by capsule count. There will be no make-up dosing for a dose that is missed due to forgetfulness or vomiting. One treatment cycle is 4 weeks. The timing of the subsequent cycles of treatment may vary depending on the disease status, and toxicities.

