Arm I	100 mg q.d. x 5 consecutive days per week for 2 weeks every 4 weeks	50 mg q.d. x 5 consecutive days per week for 2 weeks every 4 weeks	50 mg q.d. x 5 consecutive days every 4 weeks

Patients who had treatment delay > 2 weeks due to drug-related non-hematologic toxicities will also have dose reductions according to Table 3.

Dose reduction for drug-related toxicities may be undertaken temporarily or permanently for individual patients to ensure safety according to the assessment and judgment of the investigator in the following situations:

- Decrease dose by 50 mg b.i.d. (Arm A, B, C, D, F, G and Part 2) or 50 mg q.d.(Arm E, H, I) for grade 2 toxicity in a frail patient (See Appendix D)
- Decrease dose by 100 mg b.i.d. (Arm A, B, C, D, F, G and Part 2), or 100 mg q.d. (Arm E, H) or 50 mg q.d. (Arm I) for  $\geq$  grade 3 toxicity in a frail patient or a patient who has experienced more than one  $\geq$  grade 3 drug-related toxicity.

Decisions on treatment delay and dose modifications for drug-related hematologic toxicities should be guided by findings from bone marrow biopsy and/or aspirate as well as time to absolute neutrophil count (ANC) and platelet count recovery according to Table 4. Deviations from the guidelines are permitted to ensure safety and serve the best interest of the patient according to the assessment and judgment of the investigator. The reason for deviating from the guidelines should be documented in source documents.

Table 4 Guidelines on Treatment Delay and Dose Reduction for Hematologic Toxicities

Finding from bone marrow biopsy/aspirate	ANC ≥1000 and platelet count ≥100,000 by or on Day 28 of the cycle	ANC < 1000 or platelet count <100,000 on or after Day 28 of the cycle
Blasts are less than or equal to 5%	Administer study drug;  Decrease dose by 50 mg b.i.d* or 50 mg q.d.** for clinically significant and drug-related hematologic toxicity during the previous cycle	Hold study drug and repeat bone marrow when ANC and platelet count recover to baseline or better; if bone marrow blasts remains at 5% or less, continue to hold the study drug until ANC $\geq$ 1000 and platelets $\geq$ 100, 000 or until bone marrow blasts are increasing to $>$ 5%, whichever comes first; decrease by 100 mg $b$ , $i$ . $d$ * or 100 mg $q$ . $d$ .** for delay in ANC and platelet count recovery to the best level on study beyond Day 42

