Blasts are >5% but ≤ 10%	Administer study drug; decrease dose by 50 mg b.i.d.* or 50 mg q.d.** for clinically significant and drug-related hematologic toxicity during the previous cycle	For AML patients, hold study drug and repeat bone marrow in 1-2 weeks; if bone marrow blasts are decreasing, continue to hold the study drug until ANC ≥ 1000 and platelets ≥100, 000 or the recurrence of bone marrow blasts to >10%, whichever comes first; if bone marrow blasts are stable or increasing, administer the study drug; for MDS patients, hold study drug until ANC and platelet count have recovered to the best level on study or the recurrence of bone marrow blasts to >10%, whichever comes first.
		decrease sapacitabine dose by 50 mg $b.i.d*$ or 50 mg $q.d.**$ for delay in ANC and platelet count recovery to the best level on study beyond Day 42.
Blasts have decreased 25% or more from baseline but are still >10 %	Administer study drug; decrease dose by 50 mg b.i.d.* or 50 mg q.d.** for clinically significant and drug-related hematologic toxicity during the previous cycle	If ANC and platelet count have not recovered to baseline or better, hold study drug until ANC and platelet count recover to baseline or better or Day 42, whichever comes first; decrease dose by 50 mg b.i.d.* 50 mg q.d.** for clinically significant and drug-related hematologic toxicity during the previous cycle or for delay in ANC and platelet count recovery to best level on study beyond Day 42 due to drug-related hematologic toxicity
Blasts have decreased less than 25% from baseline, have increased from baseline or have increased from the best response in bone marrow	Administer study drug****	Administer study drug****

\* for patients enrolled on Arm A, B, C, D, F, G and Part 2.

\*\* For patients enrolled on Arm E, H, I.

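### Table 4's 100 mg q.d. reduction takes an Arm I patient from the 100 mg q.d. starting dose to zero

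*Combined protocol and SAP*

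**What the plan says.** Section 6.1 gives the Part 4 regimen as "Arm I: 100 mg q.d. x 5 consecutive days per week for 2 weeks every 4 weeks".

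Table 4 in Section 6.2 guides dosing after hematologic toxicity. In its first row (blasts at or below 5%), the cell for counts not recovered by Day 28 tells the investigator to hold the drug until counts recover or blasts rise above 5%. It then says to "decrease by 100 mg" b.i.d., or by 100 mg q.d. in the double-starred arms, "for delay in ANC and platelet count recovery to the best level on study beyond Day 42". The double-star footnote reads "For patients enrolled on Arm E, H, I". It makes no exception for Arm I.

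Elsewhere in Section 6.2 Arm I steps down by 50 mg:

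- Table 3 (non-hematologic toxicity) gives its first reduction as "50 mg q.d. x 5 consecutive days per week for 2 weeks every 4 weeks". Its second reduction keeps 50 mg q.d. but halves the dosing days.
- The first bullet between the two tables sets "50 mg q.d.(Arm E, H, I) for grade 2 toxicity in a frail patient".
- The second bullet separates the once-daily arms: "or 100 mg q.d. (Arm E, H) or 50 mg q.d. (Arm I) for" toxicity of grade 3 or worse in a frail patient, or for more than one such drug-related toxicity in any patient.

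**The concern.** A reduction equal to the whole starting dose is not a reduction. Followed literally, the cell stops the drug for an Arm I patient at 100 mg q.d. and gives an impossible dose for one at 50 mg q.d. Nothing in the section says that zero is meant as discontinuation.

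The patients concerned are ones the plan would want to keep on treatment. Section 4.1.1 admits Part 4 patients with 6% to under 20% marrow blasts, so an Arm I patient in this row has fallen to 5% or less. Section 6.2 also expects treatment to continue past a first reduction: removal is considered only after more than two, with an exemption for patients who are benefiting.

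Without a stated dose, sites could choose 50 mg on ten days per cycle, 50 mg on five days, or stopping. In an arm of about 20 patients that inconsistency is avoidable.

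**Working it through.** The plan does not state the dose that results from this cell, so there is no figure of its own to reproduce. The check is subtraction.

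**Inputs**

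- Starting doses: Section 6.1 and Table 3.
- Decrement: 100 mg per dose, b.i.d. or q.d. (Table 4, blasts at or below 5%, recovery delayed beyond Day 42).
- Once-daily arms covered: E, H and I (Table 4 footnote).
- Arm I escalated dose: up to 150 mg q.d. (Section 6.1.1).
- Planned numbers: about 60 patients in Part 4 (Section 3.4), randomized 1:1:1 (Section 6.1), of about 325 in all (synopsis).

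**First use from the starting dose: new dose = starting dose − 100 mg**

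| Regimen | Start | After one step | Table 3 second reduction |
|---|---|---|---|
| A, D, G | 200 mg b.i.d. | 100 mg b.i.d. | 100 mg b.i.d. |
| B, F, Part 2 | 300 mg b.i.d. | 200 mg b.i.d. | 200 mg b.i.d. |
| C | 400 mg b.i.d. | 300 mg b.i.d. | 300 mg b.i.d. |
| E, H | 300 mg q.d. | 200 mg q.d. | 200 mg q.d. |
| I | 100 mg q.d. | **0 mg** | 50 mg q.d., five days per cycle |

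Nine of the ten regimens land exactly on their Table 3 second-reduction level. Only Arm I reaches zero.

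**Arm I at other doses**

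- Already reduced: 50 − 100 = −50 mg.
- Escalated: 150 − 100 = 50 mg q.d., which is usable.
- Other Table 4 cells with a reduction use 50 mg: 100 − 50 = 50 mg q.d., also usable.

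**Arm I dose per four-week cycle**

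- 150 mg × 10 days = 1500 mg
- 100 mg × 10 days = 1000 mg
- 50 mg × 10 days = 500 mg
- 50 mg × 5 days = 250 mg

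**Reach:** 60 / 3 = 20 patients in Arm I, and 20 / 325 = 6.2%. This is the whole arm and so an upper limit. The documents do not say how many would enter the cell.

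**The case against.** The strongest reply is that the plan already contains the remedy. Table 4 is titled as guidelines, and Section 6.2 lets the investigator depart from it in the patient's interest, with the reason noted in the source documents. The second bullet is not confined to non-hematologic events, and Section 8.1 grades transfusion-dependent anemia and thrombocytopenia as grade 4. Some patients in this cell would therefore already qualify for the 50 mg Arm I step. A zero dose cannot be dispensed, so the problem would be noticed. Arm I also has the lowest dose per cycle in Part 4 (1000 mg, against 300 × 7 = 2100 mg in Arm H and 200 × 2 × 7 = 2800 mg in Arm G), so the cell may be reached less often there. All of this limits the harm. It does not correct the rule, and the bullet does not cover every patient in the cell.

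A second use of the step would also take Arms A, D and G to zero (200 to 100 to 0 mg b.i.d.). That is true, but it needs an earlier reduction. The point here is that Arm I fails on first use.

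The choice of replacement dose is also open to argument. In the other nine regimens one 100 mg step lands on the second Table 3 level, which for Arm I would be 250 mg per cycle and not 500 mg. That reading is defensible. The bullets favor 500 mg, because they give Arm I a 50 mg step even where Arms E and H take 100 mg. The decision is clinical and belongs to the sponsor.

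**Conclusion.** The concern holds. As written, this one cell gives an Arm I patient 0 mg from 100 mg q.d. and a negative dose from 50 mg q.d., although it calls for a decrease. The conclusion rests on reading the decrement as subtraction from the patient's current dose, which is how it works in every other regimen.

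The consequence is limited. It concerns an unknown part of about 20 patients: those at 100 mg q.d. or below, with blasts at or below 5% and recovery delayed past Day 42. The discretion clause allows a sensible dose, but an investigator who gives 50 mg departs from the table and should document why, while one who follows the table gives nothing. No sample size, error rate or primary analysis is touched. It should be corrected, and it can wait for the next amendment.

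**What to change.** In that Table 4 cell, keep the 100 mg q.d. decrement for Arms E and H. For Arm I, name the resulting dose: 50 mg q.d. for five days a week over two weeks of each cycle, from either 100 mg or an escalated 150 mg. Put the exception in the cell and leave the footnote alone, because the footnote also serves the 50 mg cells, which work.

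Add one sentence: for an Arm I patient already at 50 mg q.d., a further Table 4 reduction uses Table 3's second step (five dosing days per cycle).

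Resulting cuts per cycle:

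- From 100 mg q.d.: 1000 to 500 mg (50%).
- From 150 mg q.d.: 1500 to 500 mg (67%, as now).
- From 50 mg q.d.: 500 to 250 mg (50%).

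There are two side effects. At 100 mg q.d. this cell would cut no more than the 50 mg cells do, which matches how the two bullets treat Arm I. If an intermediate escalated dose such as 125 mg were used (an assumption; Section 6.1.1 sets only the 150 mg ceiling), the patient would go to 50 mg and not to 125 − 100 = 25 mg. The sponsor's clinical team should confirm the steps, including whether it prefers the 250 mg level for a patient at 100 mg q.d.

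The cost is one cell and one sentence in an amendment, with IRB/EC approval under Section 12.1. The 50 mg capsule in Section 10.1 serves both steps, so supply, randomization and analysis are unchanged.

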#### 6.3. Duration of Treatment

Patients may continue treatment at the discretion of the treating physician until they meet the criteria for terminating participation in the study (Section 4.3).

### 6.4. Post-Treatment Follow-up

All patients should be followed regularly until the resolution or stabilization of drug-related toxicity or the start of another anti-cancer treatment. Every effort will be made to conduct a post-treatment follow-up visit within 4 weeks after the last dose of the study drug or prior to the initiation of new treatment, whichever comes first. This post-treatment evaluation may be conducted over the telephone if the patient is unable to return to the clinic.

#### 6.5. Concomitant Medications and Supportive Care

Patients may not receive any other anti-cancer therapies or investigational drugs while on this study. For this study, hydroxyurea which is used to lower peripheral WBC to <50,000 at the investigator's discretion are not considered anti-cancer therapy. All concomitant medications must be recorded. Supportive treatment may include anti-emetic, anti-diarrhea, anti-pyretic, anti-histamines, analgesics, antibiotics, and blood products.

At the discretion of the treating physician, patients may take allopurinol for prophylaxis against tumor lysis syndrome. Any other prophylactic treatment for drug-related symptoms is not planned for the first dose. Thereafter, prophylaxis may be allowed for  $\geq$  grade 2 non-hematologic toxicity at the discretion of the Principal Investigator.

Prophylactic use of bone marrow growth factors is not allowed. The use of bone marrow growth factors may be allowed if its use is in compliance with the standard of care in clinical practice.

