#### 9. EFFICACY ASSESSMENT

The primary efficacy endpoint of Part 1 of this study is 1-year survival, i.e., the proportion of patients who are alive at 1-year measured from the date of the randomization. Secondary efficacy endpoints are the rate of CR, CRp, PR or CRi or hematological improvement and their corresponding durations, transfusion requirements and number of hospitalized days. The primary efficacy endpoints of Part 2 of this study are the rate of clinical benefit response (CR, CRp, PR, or major HI) and the rate of complete response (CR or CRp). Secondary efficacy endpoints are response durations, transfusion requirements, number of hospitalized days, and overall survival. The primary efficacy endpoint of Part 3 and 4 of this study is 1-year survival rate. Secondary efficacy endpoints are the rate of clinical benefit response (CR, CRp, PR, major HI or SD) and their corresponding durations, transfusion requirements, number of hospitalized days and overall survival.

The tissue samples supporting the diagnosis of AML or MDS, and the responses to sapacitabine may be submitted for central review.

Table 6 Response Criteria

Passansa Description					
Response	Description				
Complete Remission (CR) 	Normalization of peripheral neutrophils to ≥1000 /µL, platelet to ≥100,000/µL within 2 weeks of bone marrow biopsy/aspirate, and bone marrow to ≤5 % blasts; independent of transfusions*; and no extramedullary leukemia.				
Complete remission with incomplete platelet count recovery (CRp) 	Normalization of bone marrow to $\leq$ 5% blasts; peripheral neutrophils $\geq$ 1000 /µl, platelet $<$ 100,000 /µL within 2 weeks of bone marrow biopsy/aspirate; independent of transfusions*; and no extramedullary leukemia.				
Complete remission with incomplete blood count recovery (CRi) 8	Normalization of bone marrow to $\leq$ 5% blasts; peripheral neutrophils $<1000~/\mu$ L, platelet $<100,000/\mu$ L within 2 weeks of bone marrow biopsy/aspirate; independent of transfusions *; and no extramedullary leukemia.				
Partial Remission (PR) 8	Normalization of peripheral neutrophils to $\geq 1000 \ / \mu L$ , platelet to $\geq 100,000/\mu L$ within 2 weeks of bone marrow biopsy/aspirate, $\geq 50\%$ decrease in bone marrow blasts over pretreatment but still >5%; independent of transfusions * .				
Hematological improvement (HI) 9	Major response:				

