	(1) For patients with pretreatment hemoglobin < 11 g/dL, >2g/dL increase in hemoglobin; for RBC transfusion - dependent patients, transfusion - independence*				
	(2) For patients with a pretreatment platelet count <100,000/mm³, an absolute increase of ≥30,000/mm³; for platelet transfusion-dependent patients, stabilization of platelet counts and platelet transfusion independence*.				
	(3) For patients with absolute neutrophil count (ANC) $< 1,500/$ mm  before therapy, $\ge 100\%$ increase, or an absolute increase $> 500/$ mm  , whichever is greater.				
	Minor response:				
	(1) For patients with pretreatment hemoglobin < 11 g/dL, 1-2 g/dl increase in hemoglobin; for RBC transfusion – dependent patients, 50% decrease in transfusion requirements.				
	(2) Platelet response: for patients with a pretreatment platelet count $<100,000/\text{mm}^3, \ge 50\%$ increase in platelet count with a net increase $>10,000/\text{mm}^3$ but $<30,000/\text{mm}^3$ .				
	(3) For patients with absolute neutrophil count (ANC) $< 1,500/$ mm  before therapy, $\ge 100\%$ increase, but absolute increase $< 500/$ mm  .				
Stable disease (SD)**	Failure to achieve at least HI, but no evidence of clinically significant progression for > 16 weeks.				

\*independent of transfusions or transfusion –dependence refer to no packed red blood cell transfusion for 2 weeks and no platelet transfusion for 1 week .

Transfusion requirements for each patient are defined as the number of weeks during which at least one transfusion for red blood cells (RBCs) or platelets is administered and the mean number of units of RBC and platelet transfusions administered per month.

CYCLACEL LTD CONFIDENTIAL 34 of 56

\*\* for Part 2, 3 and 4 of the study only

Clinical benefit is defined as the achievement of CR, CRp, PR, major HI or SD. The duration of clinical benefit is measured from the earliest time when the patient achieved CR, CRp, PR or major HI to the first date when the major HI is lost; if the patient only achieved SD, the duration of clinical benefit is measured from the date of randomization or registration to the first date when clinically significant progression of disease is observed.

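### Table 6 discounts transfusion-supported counts but not growth-factor-supported ones, so permitted growth factors can produce a major HI or move a CRi to CRp

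*Combined protocol and SAP*

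**What the plan says.** **Growth factors.** Section 6.5 sets one restriction, "Prophylactic use of bone marrow growth factors is not allowed", and then opens other use: "The use of bone marrow growth factors may be allowed if its use is in compliance with the standard of care in clinical practice". The same section states "All concomitant medications must be recorded". Growth factors are mentioned nowhere else in the documents.

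**Response grading (Section 9, Table 6).** CR, CRp, CRi and PR each require independence from transfusions; for CR, CRp and CRi the wording is "independent of transfusions*; and no extramedullary leukemia". The footnote defines independence as "no packed red blood cell transfusion for 2 weeks and no platelet transfusion for 1 week". CR, CRp and CRi need marrow blasts of at most 5%, and PR needs at least a halving of marrow blasts. Major HI needs only a rise in hemoglobin, platelets or neutrophils, or transfusion independence in a dependent patient. It has no marrow criterion and no minimum duration.

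**Where the grades are used.**
- "Clinical benefit is defined as the achievement of CR, CRp, PR, major HI or SD" (Section 9). CRi is not in that list, nor in the CR/CRp endpoint.
- Part 2 (Section 11.2): clinical benefit and CR/CRp are co-primary. The staged rule stops at 0/12 and declares activity at 4 or more of 24, then enrolls up to 36. A further criterion calls the regimen active at 30% clinical benefit or 20% CR/CRp.
- Parts 3 and 4 (Section 11.3.1): an arm stops at 0/10 or at most 1/17 with clinical benefit.
- Part 1 MDS (end of Section 11.1.1): four or more CR, CRp, PR or major HI, with a 30-day death rate of at most 20%, permits added patients.

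**The concern.** The transfusion footnote shows that the plan does not want an externally supported count to pass as a drug effect. It applies that principle to blood products and leaves out the other count-raising support that Section 6.5 permits. Applied literally, Table 6 would credit a growth-factor rise to sapacitabine.

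Nothing downstream is sure to correct this. The trial is open label. Section 3.7 lets the investigator's disease assessment on the CRF serve as source data for the Part 2 primary endpoints, and Section 9 makes central review optional. Neutropenia and its complications are expected (Sections 1.6 and 8.2), so therapeutic use is plausible.

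At stake are two go/no-go rules built around low rates, where a few extra responses matter: the Part 2 rule against a 5% inactivity rate, and the Parts 3 and 4 futility screen.

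**Working it through.** **1. Two patients graded by Table 6 (illustrative values).**
- *Major HI.* Baseline ANC 600/mm³, then 1,300 after a myeloid growth factor given for febrile neutropenia. The rise is 700. The neutrophil clause asks for the greater of a 100% rise (here 600) and a rise above 500. Since 700 exceeds both, this is a major HI whatever the marrow shows and however short the rise.
- *CRi to CRp.* Blasts 4%, platelets 60,000/µL, ANC 800/µL, transfusion-free, no extramedullary disease: CRi, which is in neither co-primary endpoint. With ANC lifted to 1,200 the same patient is CRp and enters both.

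A third case arises at the same boundary. As written, CRi needs neutrophils below 1,000 and platelets below 100,000. A marrow remission with ANC below 1,000 but platelets of at least 100,000 fits no remission category, and a supported ANC would make it CR.

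**2. The plan's own figures.**
- Part 2, P(at least 4/24) = Σ over x = 1…12 of P(X₁ = x) × P(X₂ ≥ max(0, 4 − x)), with X₁ and X₂ each binomial(12, p). At p = 0.05: 0.3413 × 0.0196 + 0.0988 × 0.1184 + 0.0173 × 0.4596 + 0.0022 = 0.0067 + 0.0117 + 0.0080 + 0.0022 = 0.0286. At p = 0.30 it is 0.951. Both agree with the stated 5% error rates.
- Parts 3 and 4, P(stop) = (1 − p)¹⁰ + 10p(1 − p)⁹ × (1 − p)⁷. At p = 0.05: 0.5987 + 0.3151 × 0.6983 = 0.819. Table 9 gives 0.822, and its other rows agree within 0.006.

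**3. Sensitivity.** The documents give no rate of growth-factor use. The assumption is that the true clinical benefit rate is 5% and supported counts raise the apparent rate to the value in the first column. The last column carries the Part 2 rule through at least 1/12 and at least 4/24 to at least 30% of 36 (0.30 × 36 = 10.8, so 11).

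| Apparent rate | Part 2: at least 4/24 | Parts 3/4: arm stopped | Part 2: at least 11/36 |
|---|---|---|---|
| 5% | 0.029 | 0.82 | below 0.0001 |
| 6% | 0.051 | 0.76 | below 0.0001 |
| 7% | 0.080 | 0.70 | below 0.0001 |
| 10% | 0.21 | 0.53 | 0.0006 |
| 15% | 0.48 | 0.31 | 0.014 |

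One percentage point is enough to use up the 5% type I error of the 4/24 rule. The last column covers clinical benefit only. The other route, CR/CRp of at least 20% (0.20 × 36 = 7.2, so 8), is open to growth factors only through patients already in marrow remission. The documents give no rate of such near-misses, so no figure is attached to it.

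**The case against.** The strongest reply is that the exposure is narrow. Much of it stands.

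- *Marrow criteria.* A reader might infer that growth factors can by themselves produce CR, CRp or PR. They cannot: each needs a marrow response as well as the counts. Only major HI can be met on counts alone.
- *Stable disease.* In Parts 2 to 4, a patient without clinically significant progression for more than 16 weeks can count as SD. The CRi patient above might have entered clinical benefit that way, though not CR/CRp. The inflation is therefore net of such patients. For Part 2 this offset depends on SD being counted, and the opening paragraph of Section 9 omits SD from that endpoint while the other definitions include it.
- *Survival and selection.* The 1-year survival endpoint does not depend on response grading, and Section 11.3.2 chooses between schedules on it. The Part 1 AML screen uses CR plus CRi, so moving a patient from CRi to CR changes nothing there. It is touched only through the uncategorized case in step 1.
- *Between-arm bias.* A reader might infer that growth factors will be common and will favor the more myelosuppressive schedules. The documents expect schedules to differ in myelosuppression (Section 3.3) but give no frequency of growth-factor use, overall or by arm. Part 2 has one arm, and each arm in Parts 3 and 4 is screened separately against a fixed boundary.
- *The 30% criterion.* The 0.21 and 0.48 belong to the 4/24 step. Under the 30% clinical benefit criterion for 36 patients the chance stays very small. Section 11.2 nevertheless declares activity at 4/24 as well, so that step cannot be set aside.

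None of this supplies a grading rule. Barring prophylaxis reduces exposure, but the permitted therapeutic use still reaches Table 6 unfiltered.

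**Conclusion.** The gap is certain on the text; its size is unknown. As written, a growth-factor-supported rise counts as major HI, and a supported ANC can carry a marrow responder from CRi to CRp. This can inflate both Part 2 co-primary endpoints, loosen the Parts 3 and 4 futility screen, and help trigger the permissive Part 1 MDS expansion. The probabilities in the table rest on assumed inflation of a true 5% rate, net of SD. They show how sensitive the rules are and do not predict the trial's error rates. The documents do not support reading them as a 0.48 chance that an inactive regimen passes all of Part 2, nor as a bias in the survival-based choice of schedule. The point should be fixed because it concerns the definition of a co-primary endpoint and the remedy is short.

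**What to change.** Add a footnote to Table 6, parallel to the transfusion footnote:
- A neutrophil count counts toward CR, CRp, PR or HI only if no myeloid growth factor was given within a pre-specified window before it (for example 7 days).
- A hemoglobin or platelet rise counts toward HI only if no erythropoiesis- or platelet-stimulating agent was started or increased within a pre-specified window (for example 8 weeks).
- Until an unsupported count is available, the patient is graded in the category met without the supported count.

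The example windows are not from the documents; the sponsor should set and justify them in advance. Apply the rule by program from the concomitant-medication record and list growth-factor use by arm.

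This concerns grading only and leaves the treatment permission in Section 6.5 unchanged. The cost is wording and a programmed check on data already collected (Section 6.5, Table 5). The small downside is that some responses will be recorded later or lost. The absence of a minimum duration for HI is a separate matter that this footnote does not settle.
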